9.4.10.3.6 End of study/ Early termination visit

An end-of-study follow-up visit will be performed on day 180 (± 7). The following interventions will be performed:

- Physical examination
- Vital signs/Temperature
- Weight
- AE/ConMed
- Urine pregnancy test
- Safety Laboratory (Urine and Blood)
- Blood sampling for Troponin T
- Injection site reactions & systemic events/reactions assessment
- Collection subject diary
- Blood sampling for humoral immunogenicity
- Blood sampling for cellular response
- PBMC freezing and plasma aliquots

For subjects receiving 3 vaccinations, an additional end-of-study visit will be 28 (± 2 days) after the 3rd vaccination. The following interventions will be performed:

- Vital signs/Temperature
- AE/ConMed
- 12-lead ECG
- Urine pregnancy test
- Safety laboratory (urine and blood)
- Blood sampling for Troponin T
- Injection site reactions & systemic events/reactions assessment
- Collection of subject diary
- Blood sampling for humoral immunogenicity
- Blood sampling for cellular response
- PBMC freezing and plasma aliquots

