2 SYNOPSIS

Name of Sponsor/Company: University Medical Center Hamburg-Eppendorf	Individual Study Table Referring to Part of the Dossier Volume: Page:	(For National Authority Use only)
Name of Finished Product: MVA-MERS-S		
Name of Active Ingredient: MVA-MERS-S		
Title of Study:	An open, single center Phase I trial to assess the safety, tolerability and immunogenicity of two ascending doses of the candidate vaccine MVA-MERS-S	
Principal Investigator	[name]. med. [name]	
Study center:	CTC North GmbH & Co. KG at the University Medical Center Hamburg-Eppendorf [name], Germany	
Protocol-No.	UKE-DZIF1-MVA-MERS-S	
EudraCT-No.	2014-003195-23	
Study Period	Approx. 7 months per patient (screening to follow-up) Total study duration (FPFV to LPLV) approx. 13 months For subjects who gave consent for a 3 rd vaccination (= boost vaccination one year after 1 st vaccination): Approx. 10-18 months per patient (screening to follow-up) Total study duration (FPFV to LPLV) approx. 18 months total duration	
Phase of development:	Phase I, first-in-human	
Objectives: Primary Objective	
 To evaluate the safety and tolerability of two dosage levels of the experimental vaccine MVA-MERS-S. To evaluate the reactogenicity after administration of two dosage levels of MVA-MERS-S 	
Secondary Objectives	
 To evaluate MERS-S-specific antibody responses induced by two dosage levels of MVA-MERS-S 	
Exploratory Objectives	
 To evaluate MERS-S -specific cellular immune responses after administration of MVA-MERS-S To characterize MERS-S -induced B and T cell memory responses To evaluate innate cell subset phenotypes and function induced by MVA-MERS-S To evaluate early innate immunity gene expression signatures induced by MVA-MERS-S To comprehensively investigate vaccine-induced humoral immune responses and antibody functions 	
Study Design	Single-center, open-label, ascending dose phase I study	

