8.2 Primary Endpoints

The safety, tolerability, and reactogenicity of the experimental vaccine MVA-MERS-S will be measured as followed:

- Occurrence of solicited local reactogenicity signs and symptoms for 14 days following the vaccination (see Table 3)
- Occurrence of solicited systemic reactogenicity signs and symptoms for 14 days following the vaccination (see Table 4 and Table 5)
- Occurrence of unsolicited AEs for 28 days following the vaccination
- Change from baseline of safety laboratory measures
- Occurrence of SAEs throughout the study period

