9.4.10.3.4 Ambulatory Visits

Subjects will return to the study ward for ambulatory visits on study day 3, 7 and 14 (± 2), after the first vaccination and on study day 35, 42 (± 2), 56 (± 3), 84 (± 3) after the second vaccination. On the ambulatory visits the following events will be performed:

- Targeted Physical Examination (only on day 42)
- Vital signs/ Temperature
- 12-lead ECG (only on day 7, 14, 35, 42)
- Injection Site reaction & systemic events/ reaction assessment (only on day 3, 7, 14, 35 and 42)
- Safety Laboratory (Urine) (only on day 7, 14, 35, 42)
- Safety Laboratory (Blood) (only on day 3, 7, 14, 35, 42)
- Blood sampling for troponin (only on day 7, 14, 35, 42)
- Blood sampling for humoral immunogenicity (only on day 7, 14, 35, 42, 56, 84)
- Blood sampling for cellular response (only on day 14, 42, 56, 84)
- PBMC freezing and plasma aliquots
- Blood sampling for RNA storage (only on day 3, 7, 35)
- Blood sampling for innate immunity (only on day 3, 7, 35)
- Adverse events assessment
- Concomitant medication assessment
- Collection and review of diary

9.4.10.3.5 Ambulatory vaccination and subsequent ambulatory visits (only for subjects who gave consent to the study extension)

Subjects will return to the study ward for an ambulatory vaccination visit 12 months (± 4 months) after the first immunization.

The following interventions will be performed:

- Informed Consent
- I/E Criteria check
- Update medical history
- Weight
- Physical examination
- Vital signs / Temperature
- 12-lead ECG
- Injection Site reaction & systemic events/reaction assessment
- AE/ConMed
- Alcohol Breath Test
- Urine Drug Screen
- Urine Pregnancy Test
- Safety Laboratory (Urine/Blood)
- Blood sampling for humoral immunogenicity
- Blood sampling for cellular response
- PBMC freezing and plasma aliquots
- Blood sampling for RNA storage
- Blood sampling for troponin
- Blood sampling for innate immunity
- Dosing
- Training on subject diary

After dosing the following events will be performed **at 2 h, 4 h and 6 h**:

- Vital signs (and at 0 h, before dose administration)
- Temperature (and at 0 h, before dose administration)
- (AE)/ConMed (and at 0 h, before dose administration)
- Injection site reactions & systemic events/reactions assessment

Subjects will return to the study ward for ambulatory visits on study day 1, 3, 7 and 14 (± 2), after the third vaccination.

On the ambulatory visits the following events will be performed:

- Vital signs/ Temperature

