9.7.7 Serious Adverse Event (SAE) Procedures

All AEs and SAEs occurring following IMP injection and end of study visit and observed by the Investigator or reported by the subject, respectively, whether or not attributed to study intervention, will be recorded in the eCRF. All AEs that result in a subject's withdrawal from the study will be followed up until a satisfactory resolution occurs, or until a non-study related causality is assigned (if the subject consents to this).

Besides the occurrence also the relationship and intensity of these events will be determined.

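### The last visit after the third vaccination may fall on day 26 or 27, before the 28-day window for unsolicited adverse events has closed

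*Protocol*

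**What the plan says.** Two of the primary endpoints in section 8.2 are at issue: "Occurrence of unsolicited AEs for 28 days following the vaccination" and "Occurrence of SAEs throughout the study period".

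Section 9.4.10.3.6 defines two closing visits. For all subjects, "An end-of-study follow-up visit will be performed on day 180 (± 7" days). For the others, "For subjects receiving 3 vaccinations, an additional end-of-study visit will be 28" days after the third dose, with a tolerance of 2 days either way. The subject diary is collected at the second of these, and the boost visit schedule in the synopsis shows nothing after it.

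Section 9.7.7 sets the recording period: "All AEs and SAEs occurring following IMP injection and end of study visit". The sentence is awkward; I read it as from injection up to the end-of-study visit. Section 9.7.1 has AEs collected from the first administration until the defined follow-up period.

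On timing of the boost, section 9.4.10.3.5 states: "Subjects will return to the study ward for an ambulatory vaccination visit 12 months (± 4 months) after the first immunization". The synopsis gives the duration for boosted subjects as "Approx. 10-18 months per patient (screening to follow-up"). The boost schedule lists one phone call before the boost, at day ≥ -7. Only the phone-call row is ticked in that column, not the AE row.

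**The concern.** A primary endpoint with a fixed 28-day window needs an enquiry on or after day 28. The two-sided tolerance on the last post-boost visit allows the final enquiry and the diary return to come earlier. A subject can then comply fully with the protocol and still have an incomplete endpoint window. An event starting on day 27 or 28 would have no planned route into the data. The table for the third dose would claim 28 days of observation that some subjects did not have.

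The secondary question is how SAEs are found between the day-180 visit and the boost. This interval belongs to the study period of a boosted subject but contains no ward visit. The text speaks of a single end-of-study visit in section 9.7.7 while section 9.4.10.3.6 now has two, so it does not say plainly that collection continues past day 180.

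**Working it through.** **Inputs**

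- Unsolicited-AE window: 28 days after each dose (section 8.2).
- Last post-boost visit: day 28 ± 2, so day 26 to 30 (section 9.4.10.3.6).
- Visits after dose 2, which is given on day 28: day 56 ± 3, day 84 ± 3, day 180 ± 7 (main visit schedule).
- Boost: 12 ± 4 months after dose 1 (section 9.4.10.3.5). With 1 month = 365.25/12 = 30.44 days this is day 243.5 to 487, nominally 365.25.
- Screening: up to 28 days before dose 1 (section 9.5.1).

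**Reproducing the stated duration.** Duration = screening + time to boost + 28 days.

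- Shortest: (28 + 243.5 + 28)/30.44 = 9.8 months.
- Longest: (28 + 487 + 28)/30.44 = 17.8 months.

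This matches the 10 to 18 months in the synopsis. It does so only if the time between day 180 and the boost counts as study time.

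**Unobserved part of the 28-day window after the boost** = max(0, 28 − visit day), counting the visit day itself as observed.

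| Last visit on day | Days unobserved | Share of 28 |
|---|---|---|
| 26 | 2 | 7.1% |
| 27 | 1 | 3.6% |
| 28, 29 or 30 | 0 | 0% |

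**Same check for the earlier doses.**

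- Dose 1: AEs are asked on day 28 before dose 2 and at every later visit, so the window closes under observation.
- Dose 2: the day 56 ± 3 visit falls 53 − 28 = 25 to 59 − 28 = 31 days after the dose, so it can come early too. The day 84 ± 3 visit, 53 to 59 days after the dose, then covers the remainder.

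The shortfall is specific to the boost.

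**Can anything else fill it?** The second diary runs for days 15 to 28 (section 9.5.2.8.9) but is handed in at the last visit. Section 9.4.10.4 allows follow-up of an AE that is ongoing at the final visit, not detection of one that starts afterwards. Section 9.5.2.8.9 acknowledges that the tolerance on the day-42 visit can shorten recording to day 40. It makes no such statement for the boost.

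**Interval between the day-180 visit and the boost** = boost day − visit day.

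- Shortest: 243.5 − 187 = 56.5 days (1.9 months).
- Nominal: 365.25 − 180 = 185 days (6.1 months).
- Longest: 487 − 173 = 314 days (10.3 months).

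If the phone call takes place on day −7, the longest stretch without contact is 314 − 7 = 307 days and the shortest 56.5 − 7 = 49.5 days.

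**The case against.** The loss is small: none at the nominal visit and at most two days. The extension has at most 24 subjects, and the analysis is descriptive. That is fair and limits the weight of the point, but it does not remove the mismatch between the endpoint and the last permitted visit.

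On the interval before the boost, a reader might infer more than the protocol supports.

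- *That subjects have no scheduled contact.* A phone call is scheduled, although no AE enquiry is ticked for it.
- *That SAEs in the interval go unobserved.* AEs are asked at 0 h before the third dose (section 9.4.10.3.5). The standard question reaches back to when the subject was last seen or questioned (section 9.5.2.8.11). The synopsis has SAEs collected at all study visits. The weakness is recall over roughly 2 to 10 months, not absence of observation.
- *That counts in three-dose subjects are biased downward because only those who return are asked.* Every three-dose subject attended boost day 0 and was asked. A subject who stays away is not a three-dose subject. The study period without a boost is about 7 months and is closed by the day-180 visit.
- *That interval events would be entered as medical history.* Section 9.5.2.3 reserves medical history for a condition the subject forgot to mention at screening and sends findings after dosing to AEs. Section 9.7.1 defines post-dose events as AEs.
- *That follow-up after the boost is too short because dose 2 has 180 − 28 = 152 days.* The SAE endpoint sets no length of follow-up per dose, so the difference contradicts nothing.

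**Conclusion.** The point stands in a narrow form. A compliant last visit on day 26 or 27 leaves up to 2 of 28 days (7.1%) of a primary endpoint window unobserved after the third dose only. This assumes that section 9.7.7 means recording up to the end-of-study visit and that no unscheduled contact takes place after it. How many subjects would be affected cannot be known from the protocol; it depends on where visits fall within the tolerance.

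Secondarily, SAEs over about 56 to 314 days before the boost are ascertained by recall at one visit, and the protocol does not state outright that collection continues past day 180. This is a gap in clarity and in the quality of ascertainment. It is no reason to narrow the SAE endpoint to the periods with visits, because that would conflict with the continuous collection in section 9.7.1.

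**What to change.** 1. Make the post-boost end-of-study window one-sided so that it cannot open before day 28, for example day 28 to 30 or later, in section 9.4.10.3.6 and in the boost schedule. The unobserved part of the window is then 0 days. The cost is slightly less freedom in scheduling that visit.
2. State in sections 9.7.1 and 9.7.7 that, for subjects who go on to the boost, SAE collection continues past the day-180 visit until the post-boost end-of-study visit.
3. Tick AE/SAE enquiry for the pre-boost phone call already in the schedule. This adds one question to an existing contact.
4. Report events from the interval between the day-180 visit and the boost as retrospectively ascertained, and keep the SAE endpoint covering the whole study period.

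None of this adds a visit or a blood draw.

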9.4.10.4 Early Termination

All enrolled subjects who complete the study, discontinue early, or withdraw from the study will have the follow-up assessments and procedures completed for their safety as outlined in Table 1. Subjects who discontinue early or withdraw from the study will be replaced if they discontinue early or withdraw up to day 35.

In some cases it may be necessary for subjects to return to CTC North for additional care, confinement, and/or follow-up. Circumstances in which this may be necessary are:

- Follow-up on abnormal laboratory evaluations
- Follow-up on an ongoing AE at the final visit
- All additional safety follow-up visits will be at the discretion of the investigator and the sponsor.

9.5 Study Procedures and Examinations

Details regarding scheduled assessments and procedures to be conducted in this study are provided below. For detailed assessment of schedules refer to Table 1.

All relevant Laboratories involved in this trial work according to GLP. Continuous GLP compliance throughout the trial is assured.

9.5.1 Screening Procedures

Written, signed, and dated informed consent from the subject prior to the performance of any study related procedures must be obtained by an Investigator. Subjects will first have ample time to read the subject information before an investigator will start the information and informed consent process. The subject information/ informed consent process will be performed according to CTC North SOPs in groups of 2-5 subjects. Investigator will provide the subjects with information of the study and explain the nature of the study point by point. During this verbal subject information process subjects have already the opportunity to ask questions. After that, the subjects have the opportunity to individually ask questions in a one-to-one meeting with the Investigator. If the Investigator is convinced that the subject understands the nature and risks of the trial, and each subject had ample time for consideration and formulation of questions (which could also mean that the subjects first discuss the decision with friends or family members), and if all questions are answered the subject will be asked to personally sign the informed consent form. A copy or a second original of the signed informed consent form must be given to the subjects for their records.

Screening procedures must be completed between 28 days and 2 days prior to receiving the first dose of study medication. See Table 1 for a complete list of screening procedures to be performed.

Only an authorized and trained investigator may decide on the eligibility of the subject.

9.5.1.1 Screening Failure

A screening failure is defined as a subject who has given informed consent and failed to meet at least one inclusion criteria or met at least one exclusion criteria or has not been administered IMP as defined by the protocol.

Eligible subjects who meet all inclusion and no exclusion criteria but are unable to participate in the study due to scheduling conflicts/timing will not be considered screening failures.

9.5.1.2 Re-screening of Subjects

Subjects who fail to meet all inclusion criteria or meet any exclusion criterion will not be permitted to be re-screened. Screening failures will not be enrolled into the study or receive IMP and cannot be re-screened for the study at any point.

Eligible subjects who meet all inclusion and no exclusion criteria but are unable to participate in the study due to scheduling conflicts/timing may be re-screened based on investigator's discretion and sponsor's approval should their availability to participate fall outside the screening window. In these cases, a new screening number must be assigned for each subject to be re-screened and a new informed consent form signed to confirm consent for study participation.

9.5.2 Study Examinations

Assessments are to be performed according to the schedule shown in Table 1 and Table and depend on time point of IMP administration.

9.5.2.1 Safety

Safety will be evaluated by collecting reported adverse events at regular intervals throughout the study and by the assessment of physical examination findings, vital signs, clinical laboratory parameters, ECGs, and adverse events.

9.5.2.2 Medical and Medication History

A complete medical and medication history as well as demographic information will be assessed at the time-points indicated in Table 1.

The medical history will be reviewed and recorded, including:

Medical and Medication History

- Recent ingestion of medication (30 days prior to entering the screening period)
- History of respiratory, cardiovascular, renal, gastrointestinal, hepatic, endocrine, hematological, neurological, psychiatric, musculoskeletal and other diseases.

Demographic information

- Date of Birth
- Sex

9.5.2.3 Physical Examination

A complete physical examination will be performed at the time points described in Table 1.

The physical examination will include a review of the following body systems:

- General appearance
- Skin
- Head, Eyes, Ears, Nose and Throat
- Spine/Neck/Thyroid
- Musculoskeletal
- Respiratory
- Cardiovascular
- Neurological
- Abdomen (including liver and kidneys).

Any abnormalities or changes in intensity from the screening visit noted during the review of body systems have to be documented in the medical record. Clinically significant abnormal findings discovered during a physical examination after screening will be documented either as part of medical history (subject forgot to mention an intermittent medical condition at screening) or documented as an Adverse Event or part of an Adverse Event (up from the time after dose administration), if the discovered symptom is leading to a diagnosis.

9.5.2.4 Electrocardiogram

A 12-lead ECG will be done at the time points described in Table 1. Actual ECG assessment times will be documented.

Subjects must be resting in a supine position for at least 5 minutes prior to collecting the ECG. At a minimum, the date and time of when the event was performed, the investigator's assessment and the heart rate, RR, PR, QT, and QRS intervals are to be collected. All clinically significant abnormalities will be recorded on the appropriate source documents.

9.5.2.5 Vital Signs

Blood pressure should be determined by cuff (using the same method and in the same position throughout the study). Measurements of vital signs (systolic and diastolic blood pressure as well as pulse rate) will be performed after the subject has been in a sitting position for at least 5 minutes at the time points specified in Table 1. Actual vital sign assessment times will be recorded.

All measurements of vital signs must be recorded in the appropriate source documents.

Any vital sign assessment that deviates from the scheduled assessment time set forth in the protocol will be considered a protocol deviation.

Deviations from vital signs measurements are allowed as follows:

± 30 minutes (for vital sign measurements on day 0, 1, 28 and 29 and day 0 for the 3rd vaccination)

9.5.2.6 Temperature

Temperature will be measured using a digital thermometer (orally at the time points specified in Table 1).

9.5.2.7 Height and Weight

Measurements of height and weight will be performed according to the schedule in Table 1.

Height is measured in centimeters (cm) and weight is measured in kilograms (kg). Measurements are to be taken in light clothing and socks (without shoes) with pockets emptied. The subject's height is recorded to the nearest cm and weight is recorded to the nearest 0.1 kg.

Height and weight will be measured and used to calculate the BMI using the following formula:

$$\text{BMI} = \frac{\text{weight [kg]}}{(\text{height [m]})^2}$$

9.5.2.8 Clinical Laboratory Evaluations

All laboratory assays will be performed according to the laboratory's normal procedures. Reference ranges will be supplied by the laboratory and used to assess the laboratory data for clinical significance and out-of-range pathological changes. The Investigator should assess out-of-range laboratory values for clinical significance, indicating if the value(s) are not clinically significant (NCS) or clinically significant (CS). Abnormal laboratory values that are unexpected or not explained by the subject's clinical condition may be, at the discretion of the Investigator or sponsor, repeated until confirmed, explained, or resolved as soon as possible.

The following laboratory assessments will be performed:

9.5.2.8.1 Bio-Chemistry

Blood samples (4.9 mL) for serum biochemistry will be collected into a lithium heparin separator tube at the time points described in Table 1. The following parameters will be assessed:

Sodium	Aspartate transaminase (AST)
Potassium	Alanine transaminase (ALT)
Calcium	Alkaline phosphatase (ALP)
Urea	Gamma glutamyl transferase (GGT)
Creatine kinase (total)	Total bilirubin
Albumin	Glucose
Total protein	Pancreas specific amylase
Creatinine	Lactate dehydrogenase (LDH)
Creatinine clearance (MDRD) (only at Screening)	C reactive protein (CRP)

9.5.2.8.2 Hematology

A 2.7 mL sample of blood will be drawn into a tube containing potassium ethylene diamine tetra-acetic acid (**EDTA**) anticoagulant at the time points described in Table 1. The following parameters will be assessed:

Hemoglobin	Mean corpuscular hemoglobin concentration (MCHC)
Hematocrit	White blood cell (WBC) count; total and differential
Red blood cells (RBC)	Neutrophils
Mean corpuscular volume (MCV)	Lymphocytes

	Monocytes
Platelet count	Eosinophils
Mean corpuscular hemoglobin (MCH)	Basophils
Reticulocytes	

